## **C.4. Study Visits**

**Visit # 1:** During this visit, the PI will explain the study objectives, study protocol, and sequences of events and answer any remaining questions that the subject may have about the study. If after such conversation with the PI, the subject is still willing to freely participate in the study, then he/she will sign the informed consent prior to the beginning of the screening process. Specifically, subjects will obtain overview of the study and the PI will complete endothelial function assessment using EndoPat2000 device. Subjects with RHI of 2.0 or less will be eligible and will be asked to provide blood sample for triglyceride measurement. First visit will end with the collection of blood specimen and subjects will be told that the coordinator will notify them via telephone of the results for further eligibility. Only subjects with triglycerides between 150 and 400 mg/dl will be eligible to be invited to the second study visit.

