**Visit # 2:** Eligible subjects identified during visit # 1 will be asked to the CCI fasting but will be allowed to take their usual morning medications. Subjects will be instructed to start fasting at 8PM of the night before the study visit. Pregnancy test will be done to rule out pregnancy among pre-menopausal women without history of surgical sterilization. For subjects randomized to Vascepa, women who can become pregnant during the study will be asked to use a contraceptive method (i.e., hormone, intrauterine device, barrier, or abstinence) during the study and six months after the final visit. During the second visit, we will collect baseline blood samples (20 ml) for measurement of biomarkers (hsCRP, ET-1, and oxLDL); other relevant biomarkers (i.e., TNF $\alpha$ , NTproBNP, apoC3, apoA5, galectin 3, free fatty acids, relevant single nucleotide polymorphisms, and fatty acids will be measured at a later time upon securing new funding on stored blood specimens). Resting blood pressure and pulse will be measured (2x) after 15 minutes of rest and information on age, sex, race, education, height, weight will be collected. Subjects will also complete a Willett food frequency questionnaire to assess their baseline diet. Digital pulse amplitude measurements (see C.6. below) will be done. A dedicated research assistant (RA) will discuss the randomization scheme provided by the statistician with the subjects. The RA will not be blinded to the treatment assignment. Otherwise, PI, study coordinator, statistician, and other staff at the lab measuring biomarkers will all be blinded. Subjects randomized to Vascepa will know that they are taking the drug containing omega-3, since the drug is not disguised and there is no placebo (open label trial). The RA will advise subjects not randomized to Vascepa (control subjects) to continue their usual habits. Each subject randomized to EPA will receive a 12-week supply of study EPA from the BWH pharmacy with the instructions to take 4 g/d. Each subject will receive a study diary to record potential adverse effects during the next 12 weeks. Enrolled subjects will be contacted by telephone once a month by the coordinator to query about potential adverse effects and remind them of the upcoming final visit.

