For statistical analysis, we will calculate the pulse amplitude response to hyperemia for each 30-second interval as a ratio of the post-deflation pulse amplitude to the baseline pulse amplitude as described previously. The RHI will be computed by dividing the ratio obtained on the test side (side with blood pressure cuff) over the ratio obtained on the control finger. Since the peak of the RHI has been shown to occur between 90 and 120 seconds after the cuff release, we will use the average of RHIs obtained at 90 and 120 seconds post deflation for analysis. The reproducibility of this technique has been described previously. RHI is correlated with traditional brachial ultrasound and CVD risk factors. Low RHI has been associated with CAD events and improve CAD prediction beyond traditional risk factors.

In order to preserve blinding of key personnel, the PI will complete the assessment of endothelial function and an independent research assistant will share the assignment group with the study subject once all activities of study visit # 2 have been completed and PI and other staff have left the CCI. The RA will instruct the subjects assigned to Vascepa on how to obtain the study drug at the BWH research pharmacy. Furthermore, during the third visit, the RA will see all study subjects before any blinded staff and collect Vascepa bottle with remaining capsules when applicable. This way, the possibility that the PI or study staff inadvertently sees the Vascepa bottle is minimized. Subjects will be reminded not to disclose their group status to study staff other than the RA assigning the group.

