Prescreening via telephone	x		
Measurement of triglycerides	x		
Final screening visit	x		
Random allocation to EPA or no EPA and study diary		x	
PAT measurements (endothelial function) and phlebotomy	x	x	x
Demographics, height, weight, medical history, food questionnaire		x	x
Blood pressure and biomarkers (OxLDL, ET-1, and hsCRP)		x	x

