### **D. Approach to Achieve Proposed Aims**

#### **D.1. Main Aim:      **Effects of EPA on endothelial function in adults with diabetes and hypertriglyceridemia****

Initially, descriptive statistics such as the minimum, maximum, median, mean and standard deviation for each continuous variable and frequency table for each categorical variable will be used to summarize the data as well as detect outliers, data entry mistakes, and missing values. Exploratory graphical techniques such as Boxplots, Histograms, Quantile-Quantile plots, and Stem and Leaf plots will be used to further examine these data. The normality of the distribution of primary outcome of interest will be examined with a normal probability plot. The differences of baseline characteristics between EPA and placebo groups will be assessed using two sample t-tests, Chi-square tests or other non-parametric tests as appropriate. The primary analysis will be a comparison of the change in RHI from baseline to post-intervention between the 2 groups of subjects randomized to either 4g/d of EPA or no drug using a two sample t test or Wilcoxon rank-sum test. Analyses will follow the intention-to-treat principle although compliance adjusted analysis will be explored where applicable.

In addition, we will develop a general linear model including treatment and gender as the main effects, and the interaction term between treatment and gender. We will also examine

confounding by age, gender, blood pressure, smoking, exercise, body mass index, and alcohol consumption. However, due to limited sample size of this pilot study, we will evaluate each covariate separately, and the final adjusted model will include no more than 5 predictors.

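### D.1 compares an unadjusted RHI change from an undefined baseline, although two pre-treatment readings per subject are available, so the pilot's effect estimate is less precise than the collected data allow

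*Combined protocol and SAP*

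**What the plan says.** Table 3 (end of section C.7) has a row "PAT measurements (endothelial function) and phlebotomy" marked at weeks -4 to -1, week 0 and week 12. The text of C.4 agrees. At visit 1, "the PI will complete endothelial function assessment using EndoPat2000 device", and the result is used for entry: "Subjects with RHI of 2.0 or less will be eligible". At visit 2, "Digital pulse amplitude measurements (see C.6. below) will be done". Section C.6 has the research assistant "share the assignment group with the study subject once all activities of study visit # 2 have been completed", so both readings precede any knowledge of assignment and any treatment.

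Section C.6 also fixes the scoring within a session: "we will use the average of RHIs obtained at 90 and 120 seconds post deflation for analysis". Nothing is said about combining readings across visits.

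Section D.1 sets the primary analysis: "The primary analysis will be a comparison of the change in RHI from baseline to post-intervention between the 2 groups of subjects", by two-sample t test or Wilcoxon rank-sum test. Baseline RHI is not tied to a visit. C.4 uses the word baseline for visit 2 blood samples and diet, which points to week 0 but does not say so for RHI. The adjusted models consider "confounding by age, gender, blood pressure, smoking, exercise, body mass index, and alcohol consumption"; baseline RHI is not in that list.

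**The concern.** A change score from one reading carries the visit-to-visit variation of both the week 0 and the week 12 measurement. Two standard ways to reduce it are left unused: adjusting for the week 0 value instead of only subtracting it, and using the second untreated reading.

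D.1 and D.3 both describe the purpose as estimating the effect size, with its standard error, to size a confirmatory trial. D.1 also names inadequate power as a possible reason for a null result. With 15 subjects per arm, an avoidable loss of precision bears directly on that purpose.

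**Working it through.** **The plan's own figure.** D.3 gives SD 0.4, 15 per arm, 80% power and an effect size of 1.05. Alpha is not stated; I assume two-sided 0.05. Reading 1.05 as standardised (1.05 × 0.4 = 0.42 RHI units), the noncentrality is 1.05 × √(15/2) = 2.88 on 28 degrees of freedom. Power is 79.3%, so the figure reproduces.

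**Inputs not in the documents.** No between-visit correlation of RHI is given. Let a = correlation of screening with week 0, b = week 0 with week 12, c = screening with week 12, with equal variances. I take values from 0.4 to 0.8.

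**Variance per subject, in units of SD²:**
- change from week 0: 2(1 − b)
- change from the mean of both visits: 1 + (1 + a)/2 − b − c
- adjusted for week 0: 1 − b²
- adjusted for both readings: 1 − (b² + c² − 2abc)/(1 − a²)

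Example, a = b = c = 0.5: 1.00, 0.75, 0.75 and 1 − 0.25/0.75 = 0.667. SE ratios to the first are the square roots: 0.866, 0.866 and 0.816.

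| a / b / c | Mean of two, change | Adjusted, week 0 | Adjusted, both |
|---|---|---|---|
| 0.4 / 0.4 / 0.4 | 0.87 | 0.84 | 0.80 |
| 0.5 / 0.5 / 0.5 | 0.87 | 0.87 | 0.82 |
| 0.8 / 0.8 / 0.8 | 0.87 | 0.95 | 0.85 |
| 0.7 / 0.5 / 0.4 | 0.97 | 0.87 | 0.86 |
| 0.6 / 0.6 / 0.4 | 1.00 | 0.89 | 0.89 |
| 0.5 / 0.7 / 0.4 | 1.04 | 0.92 | 0.92 |

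The last three rows let screening track week 12 less well than week 0 does, which is plausible because it lies 1 to 4 weeks further away. Adjusting for both readings gives 0.80 to 0.92 throughout.

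**Entry cut at RHI 2.0.** Simulated with an assumed population mean of 1.8, SD 0.4 and equal correlations, the cut barely moves the model with both readings (0.82 at 0.5, 0.85 at 0.8). It lowers what screening adds over week 0 alone: at 0.8 the ratio of the two adjusted SEs is 0.92, against 0.85/0.949 = 0.90 without the cut. With unequal correlations the addition is close to zero (0.893 against 0.894 in the fifth row).

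**Cost of covariates.** With 30 subjects and q covariates the expected variance inflation is roughly 1 + q/(30 − q − 3). For q = 2 this is 1.08, or 1.04 on the SE; for q = 1 it is 1.038, or 1.02. Net SE ratios with both readings are 0.80 × 1.04 = 0.83 to 0.92 × 1.04 = 0.96. The visit 1 reading alone costs √(1.08/1.038) = 1.02 against its gain of 0% to 8%, so its net contribution runs from about a 2% loss to a 6% gain.

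**In RHI units, if 0.4 is the SD of change** (D.3 does not say): the planned SE is 0.4 × √(2/15) = 0.146, with 95% half-width 2.048 × 0.146 = 0.299. Multiplying by the net ratios gives SEs of 0.121 to 0.140. With 26 degrees of freedom (t = 2.056) the half-widths are 0.25 to 0.29.

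**If visit 1 is noisier.** Suppose its error variance is k times that of the other visits. With no other differences, the averaged change has variance ratio (1 + (k + 1)/4)/2. At k = 1 this is 0.75 (SE 13% smaller), at k = 2 it is 0.875 (6%), and at k = 3 it is 1.00 (no gain).

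**The case against.** Taking change from a separate week 0 reading, and not from the reading that selected the subjects, is a sound choice. It leaves within-arm changes free of the direct selection effect, and the between-arm comparison is unbiased. That stands: the issue is efficiency only. A reader might infer that the two visits' difference in selection makes the analysis invalid, or that using visit 1 would bias the comparison. Neither follows. The cut at 2.0 is applied before randomisation and equally to both arms.

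A reader might also infer that averaging the two readings would cut the SE by 14% to 16%, worth about a third more subjects. The documents do not support this as a general figure. It needs equal correlations across unequal intervals and interchangeable visits. C.4 requires fasting for visits 2 and 3 but gives no such instruction for visit 1. C.6 says PAT is done fasting, but refers back to text that outlines it only for the later visits. The table shows the averaged change gaining nothing, or losing 4%, under modest departures from equal correlation.

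Finally, that the plan means a single visit 2 baseline is an inference, though the natural one. What the text establishes firmly is that baseline RHI is undefined. The documents also give no figure for how variable RHI is between visits.

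**Conclusion.** The concern holds as a loss of precision, not as a flaw in validity. D.1 leaves baseline RHI undefined, plans no adjustment for it and uses the screening reading only for entry. Under assumed correlations of 0.4 to 0.8, modelling both pre-treatment readings as covariates makes the SE of the treatment difference about 8% to 20% smaller than the single-baseline change score, or about 4% to 17% after the cost of two covariates.

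In most settings the bulk of this comes from adjusting for week 0 RHI. Only when all three correlations are high and equal (about 0.7 to 0.8) does the screening reading approach or exceed half of the gain. The sizes rest on correlations that the documents do not give. The direction for the two-covariate model did not change in any setting tried.

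**What to change.** In D.1:
- Define baseline RHI as the visit 2 (week 0) reading.
- Make the primary between-arm estimate, with its standard error and confidence interval, come from a linear model of week 12 RHI (or change) on treatment, with visit 2 RHI and visit 1 RHI as separate covariates. Both should be scored by the 90/120-second rule in C.6. Three predictors fit within D.1's limit of five.
- Report within-arm changes from visit 2 only, since visit 1 values are selected to be low and would exaggerate increases.
- Do not use a plain average of the two visits unless measurement conditions, including fasting, are shown to match. State in C.4 whether visit 1 PAT is done under the C.6 conditions.

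Fix the wording before unblinding. If visit 1 tracings cannot be scored by the C.6 rule, adjusting for visit 2 alone would in most settings keep most of the gain.

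The cost is SAP wording, scoring of visit 1 tracings already recorded, and two model degrees of freedom. No new visit or measurement is needed. The adjusted effect will not equal the simple difference of the two reported arm changes, and the report should say so.

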## **D.2. Secondary Aim:      **Effects of EPA on CVD biomarkers in subjects with DM and hypertriglyceridemia****

Same approach as in the primary aim will be used for the secondary aim. Briefly, the distribution of each outcome variable will be examined and Box-Cox transformations may be applied. A two sample t-test or Willcoxon rank sum test will be used to compare each outcome between treatment and control groups. A multiple linear regression model will be used for adjusted analysis. Due to the small sample size, potential confounding factors will be assessed separately and may be included in the final model when applicable.

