## **C.3. Randomization Scheme**

Randomization will occur during the second study visit at the CCI for those who meet eligibility criteria. In this pilot study, 30 subjects will be randomized with equal probability to EPA intervention (n=15) or no EPA (no drug) (n=15) stratified according to gender. Permuted blocks (block size of 2) will be used to achieve groups of equal size. We will create blocks within each gender and each ethnicity (Caucasian, African- American, and others) to assure balance distribution of gender and ethnicity between the two groups.

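### D.2 does not say whether Box-Cox applies to biomarker levels or to their changes, and does not adjust for baseline; log-scale ANCOVA would settle both at almost no cost

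*Combined protocol and SAP*

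**What the plan says.** - Section D.2 opens by importing the primary method: "Same approach as in the primary aim will be used for the secondary aim".
- Section D.1 defines that method: "The primary analysis will be a comparison of the change in RHI from baseline to post-intervention between the 2 groups", by two-sample t-test or Wilcoxon rank-sum test.
- D.2 then says that "the distribution of each outcome variable will be examined and Box-Cox transformations may be applied". It gives no rule for choosing the power, no shift constant, and no order for transforming and differencing.
- On the test, D.2 says: "A two sample t-test or Willcoxon rank sum test will be used to compare each outcome between treatment and control groups". The word change does not appear in D.2.
- On adjustment, D.2 says: "A multiple linear regression model will be used for adjusted analysis". The covariates listed in D.1 are age, gender, blood pressure, smoking, exercise, body mass index and alcohol. Neither section names the baseline value of the outcome.
- Table 3 schedules oxLDL, ET-1 and hsCRP at weeks 0 and 12, so a baseline value is planned for every randomized subject. Section C.3 randomizes 15 per arm.

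**The concern.** Box-Cox requires strictly positive data. A plasma concentration meets that requirement; a change in concentration does not. By cross-reference to D.1 the quantity compared is the change, so if the transformation were meant for that quantity, the only remedy D.2 names for skewness could not be carried out.

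The text leaves at least three analyses open: raw change, change in transformed levels, and the transformed week-12 value alone. They differ in power and in the units of the result.

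Even where Box-Cox can be computed, the power is estimated from the data and may differ between hsCRP, ET-1 and oxLDL. Only the log (power zero) turns a difference into a ratio that means the same at every level. On a square-root scale, a fall of one unit takes 9 to 4 (ratio 0.44) or 4 to 1 (ratio 0.25). One transformed effect then corresponds to different proportional effects, which is awkward for planning another trial.

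Finally, leaving the baseline value out of the model gives up precision that the design has already paid for.

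**Working it through.** **The plan's own figure.** D.3 gives 80% power for an effect size of 1.05 with 15 per arm. Alpha is not stated; I take 0.05 two-sided. With noncentrality 1.05 × √(15/2) = 2.88 and 28 degrees of freedom, power is 79.3%, so the figure reproduces when 1.05 is read as a standardised difference (0.42 RHI units at SD 0.4). It concerns RHI only. No SD, correlation or expected effect is given for any biomarker, so every biomarker input below is an assumption.

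**Can Box-Cox be applied to changes?** With no treatment effect and the same distribution at both visits, a change is negative with probability 0.5. The chance that all 15 control-arm changes are positive is 0.5^15 = 0.00003. In simulation, every trial contained at least one negative change, and a standard Box-Cox routine rejects such data.

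**What baseline adjustment adds.** Let σ be the SD of the log level and ρ the correlation between visits. The per-subject variances are:
- change: 2σ²(1 − ρ)
- week 12 alone: σ²
- ANCOVA: σ²(1 − ρ²)

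The ratio of ANCOVA to change is (1 + ρ)/2, which is 0.75 at ρ = 0.5, 0.85 at 0.7 and 0.90 at 0.8.

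Example: σ = 1.0, ρ = 0.7, level halved (ln 2 = 0.693).
- Change: SD √0.6 = 0.775; 0.693/0.775 = 0.895; noncentrality 0.895 × √7.5 = 2.45; power about 66%.
- ANCOVA: SD √0.51 = 0.714; 0.693/0.714 = 0.971; noncentrality 2.66; power about 73% on 27 degrees of freedom, before a small loss for chance baseline imbalance.

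**Simulated power.** Lognormal levels, 15 per arm, 2,000 to 10,000 trials per scenario; two values are shown where repeat runs differed. The Box-Cox column uses one power per trial, estimated from both visits pooled.

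| log-SD, ρ, EPA/control ratio | raw change, t | raw change, Wilcoxon | Box-Cox on levels, change t | log change, t | log ANCOVA |
|---|---|---|---|---|---|
| 0.3, 0.7, 0.8 | 63% | 61% | not run | 72% | 77% |
| 0.8, 0.5, 0.5 | 35% | 42% | 61% | 62% | 72–74% |
| 0.8, 0.7, 0.5 | 48% | 59% | 84% | 84% | 88% |
| 1.0, 0.5, 0.5 | 20–21% | 28–29% | 45% | 45% | 54–55% |
| 1.0, 0.7, 0.5 | 29–30% | 42% | 64% | 65% | 71–73% |

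- **Box-Cox on levels against log:** about 1 point or less.
- **ANCOVA against Box-Cox on levels with change scores** (same run): 72 − 61 = 11, 88 − 84 = 4, 54 − 45 = 9, 72 − 64 = 8 points. At ρ = 0.8, log-SD 1.0 and ratio 0.5, the gain over the log change is 85.5 − 83.3 = about 2 points.
- **ANCOVA against the raw-change t-test:** 77 − 63 = 14 points with mild skew. With strong skew it runs from 55.1 − 20.6 = 34.5 to 73 − 29 = 44.
- **Week 12 alone, log scale:** 45% at log-SD 1.0, ρ = 0.7, ratio 0.5, against 65% for the log change and 71% for ANCOVA.
- **Type I error with no effect:** 3.6% to 5.3% across the methods.

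**The case against.** A reader might infer that the plan contradicts itself and that skewed biomarkers will therefore be tested as raw changes, at perhaps 20–48% power. The documents do not support that.

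- **The reading.** D.2 never says that changes are transformed. The outcomes are positive concentrations, and a plan that names Box-Cox is reasonably read as applying it where it can be computed. Raw changes are not named as a fallback, and regression is also allowed.
- **The comparison.** On that reading Box-Cox performs about as well as the log. Setting raw changes against log ANCOVA combines the gain from transforming with the gain from baseline adjustment. Only the second remains, and it shrinks as the correlation between visits rises.
- **Effect sizes.** It would also go too far to say that no interpretable effect size results. Raw changes give a mean difference in native units with a standard error. The effect-size goal in D.1 and D.3 is framed around endothelial function, and no biomarker power is claimed.
- **Preference.** Fixing the log for all three markers in advance is itself an assumption.

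All of this stands against the stronger reading. It does not remove the gap: D.2 states neither the scale nor the order of operations, and it leaves out an available baseline covariate. The Wilcoxon option recovers part of the loss on raw changes when skew is strong (30% to 42% in the last row of the table) and none when it is mild (63% against 61%).

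**Conclusion.** The point holds as a gap in specification with a better method available at almost no cost. It is not an internal contradiction, nor a stated intention to analyse raw changes. Box-Cox on changes cannot be computed. Box-Cox on levels can, at little cost in power but on scales that may differ by biomarker.

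The gain from log ANCOVA is about 4 to 11 points over change scores on transformed levels (log-SD 0.8–1.0, ρ 0.5–0.7, level halved), falling to about 2 points at ρ = 0.8. The gain of 14 to 44 points applies only if raw changes were in fact tested by t-test. All these figures rest on assumed lognormal levels, SDs, correlations and ratios.

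The issue is the efficiency and interpretability of an exploratory secondary aim in a 30-subject pilot. Type I error is not affected. I class it as a free improvement.

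**What to change.** In D.2, replace the sentence on Box-Cox and the sentence on the test with wording to this effect: *hsCRP, ET-1 and oxLDL will be log-transformed as levels at each visit. Log week-12 values will be compared between arms by ANCOVA adjusted for the log baseline value, and the ratio of geometric means (EPA/control) will be reported with its 95% CI. A Wilcoxon rank-sum test on the change in log level will be a sensitivity analysis.*

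The Wilcoxon test should be on the log change because ranks of raw and log changes differ. It also guards against a marker for which the log is a poor choice.

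The cost is a wording change and one degree of freedom for the baseline covariate. No new samples or assays are needed, since Table 3 already schedules both measurements.
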